3.7.2.3 Description of OAC treatment patterns

In longitudinal analysis during the study period, in AF patients exposed to VKA, apixaban, rivaroxaban, and dabigatran, we will describe the OAC treatment patterns, using a treatment sequence analysis, to define lines of treatment (LOT), switches of OAC, concomitant treatments and temporary or permanent discontinuation. We will use an adaptation of Sankey diagrams for the visualization. We will define the dominant therapeutic management and characterize prescription fills. Patients must have received at least one delivery of apixaban, dabigatran, rivaroxaban, VKA within the entire follow-up to be included in the treatment pattern analyses. Other information such as prescriber's characteristics at each coverage period (hospital or private medical practice and prescriber's specialty) and the type of AF treatment(s) used will be considered.

The treatment pattern analysis will provide the following information:

- Number and percentage of patients receiving each of OAC treatment
- Percentage of patients who received 1, 2, 3, 4 and 5+ LOTs during the follow-up
- Analyses of duration of treatment by LOT
- Time to next treatment (TTNT) changed by line of treatment

Persistence rate to OAC at 6 and 12 months after the initiation will be estimate by Kaplan-Meier curves

3.7.2.4 Description of the therapeutic management before/after the first stroke occurring after initiation of OAC therapy

To describe the therapeutic management before/ after the first stroke in AF patients exposed to dabigatran,

apixaban, rivaroxaban, VKA and unexposed to OAC i.e. 5 classes, in cross-sectional analysis at 6 and 12 months before and after the first stroke, we will describe HCRU (ambulatory care, hospital care, rehabilitation care facilities and medications) defined in Table A1. 2.

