End date of unexposed sequence	
Date variable
 
The end date of unexposed sequence is defined as:
 
 – The day before the Start date of treatment sequence if the patient starts an OAC 
OR
 
 – End of follow-up period in other cases

Second, each event of interest with the occurred dates available in the data extraction for the AF patients in France during their follow-up will be derived by treatment exposure sequence as indicated in [Table VIII](#).

Table VIII. Derived variables for identifying events of interest

Variable	Definition
Stroke (ischemic or hemorrhagic)	
Binary variable (Yes / No)
 
Equals to “Yes” if the patient is hospitalized with any discharge diagnosis (i.e., main, related or associated diagnosis) of stroke (ischemic or haemorrhagic)

	
ICD-10 codes: I60.x, I61.x, I62.9, I63.x, I64.x, G45.x, G46.x, G81.x, S06.4, S06.5, S06.6
 
Equals to “No” in other cases

Major bleeding	
Binary variable (Yes / No)
 
Equals to “Yes” if the patient is hospitalized with any discharge diagnosis (i.e., main, related or associated diagnosis) of major bleeding
 
ICD-10 codes: I60.x, I61.x, I62.9, S06.4, S06.5, S06.6, I85.0, K22.6, K25.0, K25.2, K25.4, K25.6, K26.0, K26.2, K26.4, K26.6, K27.0, K27.2, K27.4, K27.6, K28.0, K28.2, K28.4, K28.6, K29.0, K62.5, K92.0, K92.1, K92.2, D62, H35.6, H43.1 H45.0, H92.2, I31.2, J94.2, R04.x, K66.1, M25.0, N02, N93.8, N93.9, N95.0, R31, R58, T79.2
 
Equals to “No” in other cases

Death	
Binary variable (Yes / No)
 
Equals to “Yes” if the date of death is reported in DCIR
 
Equals to “No” in other cases

Date of occurrence	
Date variable
 
Equals to the value of date when occurred the event

In the case of a patient presents an event of interest during the grace period, which ends after the end of the study, the event will be considered neither in an exposed nor in an unexposed period, and the patient will be censured at the end of the study period.

Then, the variable presented in [Table IX](#)[Table X](#) will be derived for the analyses of incidence, for each patient, for each event of interest and for each exposure treatment sequence.

Table IX. Derived variables for the analyses of incidence rate on events of interest

Variable	Definition

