Time period	
Categorical variable (“From 12 to 6 months before 1st stroke date”/ “From 6 months to the 1st stroke date” / “From 1st the stroke date to 6 months after” / “From 6 to 12 months after the 1st stroke date”)
 
Equals to “From 12 to 6 months before 1st stroke date” if date of care indicated in the data extraction and associated with the reimbursement is between 12 months and 6 months before 1st stroke
 
Equals to “From 6 months to the 1st stroke date” if date of care indicated in the data extraction and associated with the reimbursement is between 6 months and 1st stroke
 
Equals to “From 1st the stroke date to 6 months after” if date of care indicated in the data extraction and associated with the reimbursement is between 1st stroke and 6 months after 1st stroke
 
Equals to “From 6 to 12 months after the 1st stroke date” if date of care indicated in the data extraction and associated with the reimbursement is between 6 months and 12 months after 1st stroke

Number of occurrences	
Continuous variable
 
Equals to the number of occurrences where the two criteria are met:
 
 – The variable HCRU after first stroke equals to the specified HCRU after first stroke – The value of the variable Date of care falls in the specified time period
------------------------------	--

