Min - Max	xx.x - xx.x	xx.x - xx.x	xx.x - xx.x	xx.x - xx.x	xx.x - xx.x
From 6 to 12 months after the 1 st stroke date					
n* (%)	xx (x.x)	xx (x.x)	xx (x.x)	xx (x.x)	xx (x.x)
Mean (std)	xx.x (xx.x)	xx.x (xx.x)	xx.x (xx.x)	xx.x (xx.x)	xx.x (xx.x)
Median	xx.x	xx.x	xx.x	xx.x	xx.x
Q1 - Q3	xx.x - xx.x	xx.x - xx.x	xx.x - xx.x	xx.x - xx.x	xx.x - xx.x
Min - Max	xx.x - xx.x	xx.x - xx.x	xx.x - xx.x	xx.x - xx.x	xx.x - xx.x
Ambulatory care					
....					
Hospital care					

	Apixaban (N=XXX)	Dabigatran (N=XXX)	Rivaroxaban (N=XXX)	VKA (N=XXX)	All exposed (N=XXX)
--	---------------------	-----------------------	------------------------	----------------	------------------------

....
**Rehabilitation care facilities
(SSR)**
....

....
Medications related to AF
....

*N: number of patients with at least one reimbursement of the specific OAC during the follow-up
 n: represent the number of patients with at least 1 HCRU and at least one reimbursement of specific OAC during the time-period considered

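### Objective 7, Table A17: the stroke day falls in two windows, and the rules for N and n let OAC stopping, switching or recent initiation show up as a change in care around the stroke

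*SAP*

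**What the plan says.** Objective 7 describes management before and after the first stroke occurring after OAC initiation. SAP 9.4.3.6, Table XIX, places each item of care in one of four levels of a single categorical variable, Time period. The last pre-stroke level applies when the date of care "is between 6 months and 1st stroke". The first post-stroke level applies when it "is between 1st stroke and 6 months after 1st stroke". No rule says which level owns the stroke day.

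The stroke itself is a hospital stay: the event is present "if the patient is hospitalized with any discharge diagnosis (i.e., main, related or associated diagnosis) of stroke (ischemic or haemorrhagic"). In Table XIX any hospital admission counts as hospital care, and nothing sets the index stroke stay aside.

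The footnote to Table A17 (SAP Appendix 3, section 3.7) defines the column total N as the "number of patients with at least one reimbursement of the specific OAC during the follow-up". It defines the window count n as the "number of patients with at least 1 HCRU and at least one reimbursement of specific OAC during the time-period considered". SAP 9.7.4.6 describes the same analysis but asks only for at least one HCRU reimbursement, with no OAC condition.

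Protocol 3.7.2.4 names the groups as dabigatran, "apixaban, rivaroxaban, VKA and unexposed to OAC i.e. 5 classes, in cross-sectional analysis at 6 and 12 months before and after the first stroke". Table A17 has four drug columns and an all-exposed column.

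**The concern.** The objective is read by comparing rows within a column: care in the months before the stroke against care in the months after. That comparison needs windows that do not overlap, a group fixed before the event, and a count that depends on care alone. None of the three is secured.

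- **Windows.** The stroke day carries the largest single item of hospital care in the period, and it may be booked as prior care, as subsequent care, or as both.
- **N.** Follow-up continues past the stroke, so a drug first dispensed afterwards puts the patient in that drug's column, including its pre-stroke rows.
- **n.** A patient who used care but had no fill of that drug in the window is not counted. A fall in n/N after the stroke may therefore reflect less care or a change of anticoagulant, and the table cannot tell which. In the same way, a patient whose first OAC dispensing was less than 6 months before the stroke is in N but cannot enter n for the 12-to-6-month row.

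The shell matters because SAP 9.6 says that results will be reported automatically in the format of the table shells.

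**Working it through.** The plan gives no target figure for this descriptive objective, so there is nothing to reproduce. The check applies the written rules to dated records and then to a small assumed cohort.

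**Step 1: windows.** Inputs are the four levels in Table XIX, read with inclusive limits, with 6 months taken as 183 days and the stroke as day 0.

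| Day | Levels met |
|---|---|
| −183 | 12 to 6 months before; 6 months to stroke |
| −1 | 6 months to stroke |
| 0 | 6 months to stroke; stroke to 6 months after |
| +1 | stroke to 6 months after |
| +183 | stroke to 6 months after; 6 to 12 months after |

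Three days meet two levels of a variable that can hold only one. Day 0 is the one that matters most. Suppose the stay is dated to the stroke, the limit is inclusive, and no OAC fill is required for n. Then the share with hospital care in the 6 months before stroke is 100%, whatever the true prior share. With day 0 excluded it is the true share: 10%, 20% or 40% if those values are assumed. Under the Table A17 footnote the 100% does not follow, because n also needs a fill of the drug in the window.

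**Step 2: columns.** Assumptions, none of them from the documents:
- 100 patients are on VKA at stroke, had never used apixaban, and all use care in every window.
- Afterwards a = 20% switch to apixaban and s = 10%, 30% or 50% stop.
- Neither group has a VKA fill in the post-stroke window considered.

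Formulas from the footnote:
- N(VKA) = 100 and N(apixaban) = 100a = 20, so the columns sum to 120 for 100 patients.
- Pre-stroke n(VKA) = 100 and n(apixaban) = 0.
- Post-stroke n(VKA) = 100(1 − s − a) and n(apixaban) = 20.

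| s | VKA n/N before | VKA n/N after | Apixaban n/N before | Apixaban n/N after | In no drug's post-stroke n |
|---|---|---|---|---|---|
| 10% | 100/100 | 70/100 | 0/20 | 20/20 | 10 |
| 30% | 100/100 | 50/100 | 0/20 | 20/20 | 30 |
| 50% | 100/100 | 30/100 | 0/20 | 20/20 | 50 |

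Care use is constant by construction, yet the VKA column falls to between 30% and 70% and the apixaban column rises from 0% to 100%. If instead 20–40% of 1,000 VKA patients stop or switch, again an assumption, post-stroke n loses up to 1,000 × 0.20 to 1,000 × 0.40 = 200 to 400.

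**Step 3: text against shell.** Under the rule in SAP 9.7.4.6 (at least one HCRU reimbursement), each of the 100 patients counts in n in every window. The shell removes some of them. The two places in the SAP therefore give different numbers for the same table cell.

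**The case against.** The other side is right on several points.

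- A reader might infer that post-stroke switchers appear as users of care in the new drug's pre-stroke rows. They do not: with no fill of that drug before the stroke they add nothing to n. They enter only N.
- A reader might infer that patients who stop OAC disappear from the table. They stay in N, and they leave n only if they have no fill of that drug in the window. One refill within 6 months after the stroke keeps them in the first post-stroke row.
- A reader might infer that every patient will show hospital care before the stroke. That needs the inclusive limit, a stay dated to the stroke, and no OAC condition on n. Since Time period is categorical and the post-stroke label begins at the stroke date, a programmer could equally put day 0 after the stroke.
- A reader might infer that the SAP wrongly deleted the protocol's unexposed class. The objective is limited to strokes after OAC initiation, SAP Table XXI limits the population to incident patients exposed to OAC, and protocol 3.5.2 defines unexposed as AF without OAC treatment. The inconsistency lies between protocol 3.7.2.4 and the objective's own wording.
- The objective is secondary and descriptive, with no before/after test, and switching and stopping are reported under objective 5, though not in relation to the stroke.

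What these points leave untouched is the unowned stroke day, the overlapping denominators partly set by later treatment, and the contradiction between the shell and section 9.7.4.6.

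**Conclusion.** The point holds in this bounded form. Table XIX does not say which window owns the stroke day, so the index admission can count as prior hospital care. Table A17's N takes in post-stroke treatment, so drug columns overlap and switchers enlarge the new drug's pre-stroke denominator while adding nothing to its n. Table A17's n contradicts SAP 9.7.4.6, and under it n/N responds to stopping, switching and recent initiation as well as to care use.

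The size cannot be estimated from the documents, which give no stopping or switching rate after stroke. The 70, 50 or 30 of 100 and the column sum of 120 rest on assumed rates and on no VKA fill in the window for those who stop or switch. The 100% hospital-care figure is conditional as stated above and should not be cited without its conditions. No test or sample size is affected. This should be corrected before programming, because as written the before/after rows cannot be read as a change in care.

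**What to change.** 1. End the last pre-stroke window on the day before the stroke admission. Put the index stroke stay in the post-stroke window or on its own line. Make the 6-month limits non-overlapping as well, and state that the stroke date is the admission date.
2. Limit the table to patients with a first stroke after OAC initiation. Assign each patient once, by the Table VII sequence covering the day before the stroke: VKA, apixaban, dabigatran, rivaroxaban, or initiated but off OAC at stroke. SAP 9.4.2 gives a stroke in a grace period running past study end to neither state, so say where those patients go.
3. Define n as patients with at least one HCRU in the window, as in SAP 9.7.4.6, and delete the OAC condition from the footnote.
4. Use as denominator the patients of that group still under follow-up in the window, or report rates per patient-month. A fixed N would keep patients who had died or been censored (SAP 9.2.1.4) in the later rows.
5. Reconcile the five classes in protocol 3.7.2.4 with the objective wording and the Table XXI population. The off-OAC group in step 2 consists of patients who had started OAC, so it is not the protocol's unexposed class.

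The cost is SAP and footnote wording, one more column and minor reprogramming. Table VII already yields the dated sequences.

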3.8. Sensitivity analyses

All results associated to the sensitivity analyses are notified in the previous tables.
